1	Care setting	Categorical care setting for elranatamab or teclistamab administration Inpatient (IP) Non-IP Pharmacy	Index date, second treatment date, third treatment date, and overall

Objective	Variable	Definition	Assessment Period(s)
1	Time since MM diagnosis	Time (in months) from first MM diagnosis to index date (continuous)	MM diagnosis to index date
1	Income	Categorical household income	Index date
1	Education	Categorical level of highest education completed:	Index date
1	Marital Status	Categorical marital status:	Index date
1	Home Ownership	Categorical home ownership status: Renter Owner Unknown	Index date
1	Triple class exposed ¹⁷	 Medical claim in the IP, Non-IP or pharmacy setting with an NDC, HCPCS, Current Procedural Terminology (CPT), generic name, or ICD-10 procedure code for all the following therapies in the inpatient, non-IP, or pharmacy setting (dichotomous): ≥ 1 claim for PIs (see generic names below) ≥ 1 claim for IMiDs (see generic names below) ≥ 1 claim for CD38 mAbs (generic names: daratumumab, isatuximab) 	MM diagnosis to 1 day prior to index date
1	Penta-drug exposed ¹⁷	Medical claims with an NDC, HCPCS, CPT, generic name, or ICD-10 procedure codes in the inpatient, non-IP or pharmacy setting for all of the following therapies(dichotomous): • ≥ 2 distinct claims for PIs (see generic names below) • ≥ 2 distinct claims for IMiDs (see generic names below) • ≥ 1 claim for CD38 mAbs (generic names: daratumumab, isatuximab)	MM diagnosis to 1 day prior to index date

Objective	Variable	Definition	Assessment Period(s)
1	Hematopoietic Stem Cell Transplantation	Medical claim with an HCPCS, CPT, or ICD-10 code for hematopoietic stem cell transplantation in the inpatient, non-IP setting (dichotomous)	MM diagnosis to 1 day prior to index date
1	BCMA-directed therapy	Medical claim with an NDC, HCPCS CPT, generic name or ICD-10 procedure code in the inpatient, non-IP, or pharmacy setting for idecabtagene vicleucel, ciltacabtagene autoleucel, or belantamab (dichotomous)	MM diagnosis to 1 day prior to indexhe date Index date to the end
			of follow-up
1	CAR-T	Medical claim with an NDC, HCPCS, generic name or CPT code in the inpatient, non-IP, or pharmacy setting for idecabtagene vicleucel or ciltacabtagene autoleucel (dichotomous)	MM diagnosis to 1 day prior to index date
		autoreucer (dienotomous)	Index date to the end of follow-up

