1	Talquetamab	Medical claim with an NDC, HCPCS, generic name or CPT code in the inpatient, non-IP, or pharmacy setting for talquetamab (dichotomous)	MM diagnosis to 1 day prior to index date
			Index date to the end of follow-up
1	PIs	Medical claim with an NDC, HCPCS, generic name or CPT code in the inpatient, non-IP, or pharmacy setting for bortezomib, carfilzomib, or ixazomib	MM diagnosis to 1 day prior to index date
		(dichotomous)	Index date to the end of follow-up
1	IMiDs	Medical claim with an NDC code or generic name in the non-IP or pharmacy setting for lenalidomide, thalidomide, or pomalidomide (dichotomous)	MM diagnosis to 1 day prior to index date
			Index date to the end of follow-up
1	Steroids	Medical claim with an NDC, HCPCS, generic name or CPT code in the inpatient, non-IP, or pharmacy setting for dexamethasone, methylprednisolone, prednisone, or prednisolone (dichotomous)	MM diagnosis to 1 day prior to index date
		prediffication, or prediffication (dieffotolificas)	Index date to the end of follow-up

Objective	Variable	Definition	Assessment Period(s)
1	mAbs	Medical claim with an NDC, HCPCS, generic name or CPT code in the inpatient, non-IP, or pharmacy setting for daratumumab, isatuximab, or elotuzumab (dichotomous)	MM diagnosis to 1 day prior to index date
			Index date to the end of follow-up
1	Chemotherapies	Medical claim with an NDC, HCPCS, generic name or CPT code in the inpatient, non-IP, or pharmacy setting for doxorubicin hydrochloride, melphalan, bendamustine, cyclophosphamide, etoposide, or	MM diagnosis to 1 day prior to index date
		cisplatin (dichotomous)	Index date to the end of follow-up
1	Small molecule inhibitors	Medical claim with an NDC, HCPCS, generic name or CPT code in the inpatient, non-IP, or pharmacy setting for venetoclax (dichotomous)	MM diagnosis to 1 day before index date
		setting for venerociax (dichotomous)	Index date to the end of follow-up
1	Nuclear export inhibitors	Medical claim with an NDC, HCPCS, generic name or CPT code in the inpatient, non-IP, or pharmacy setting for selinexor (dichotomous)	MM diagnosis to 1 day before index date
		coming for community (controlled as)	Index date to the end of follow-up
1	Antivirals	Medical claim with an NDC, HCPCS, generic name or CPT code in the inpatient, non-IP, or pharmacy setting for antiviral medications (dichotomous)	14 days prior to index date to 1 day prior to index date

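### Penta-drug exposed counts claims instead of agents, so three drugs can satisfy a five-drug label

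*Protocol*

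**What the plan says.** Protocol section 9.3, Table 2, has two neighbouring rows on prior exposure.

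- **Triple class exposed:** "≥ 1 claim for PIs (see generic names below", "≥ 1 claim for IMiDs (see generic names below" and "≥ 1 claim for CD38 mAbs (generic names: daratumumab, isatuximab".
- **Penta-drug exposed:** "≥ 2 distinct claims for PIs (see generic names below", "≥ 2 distinct claims for IMiDs (see generic names below" and again "≥ 1 claim for CD38 mAbs (generic names: daratumumab, isatuximab".

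Both use the same look-back, "MM diagnosis to 1 day prior to index date". The agents are named in later rows of the table: for PIs, "setting for bortezomib, carfilzomib, or ixazomib"; for IMiDs, "lenalidomide, thalidomide, or pomalidomide (dichotomous".

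Annex 2 lists codes by class and has no separate entry for penta-drug exposure. Both variables belong to primary Objective 1, which covers treatment history.

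**The concern.** The label and the 2 + 2 + 1 structure point to five drugs: two PIs, two IMiDs and one anti-CD38 antibody. The text asks for two claims in each of the first two classes and never says that they must be for different agents. PIs and IMiDs are given or filled repeatedly, so a patient can collect two claims on a single drug.

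At stake is one reported percentage. Treatment history is part of a primary objective in a study that is wholly descriptive, so this percentage is itself a result. If coded as written, it would be published under a label that some of the flagged patients do not meet. Exploratory Objective 3 repeats all objectives in the teclistamab cohort, so the same figure would be affected there.

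**Working it through.** The protocol gives no figure for this variable, so there is nothing to reproduce. The check has three parts.

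**1. Minimum number of drugs.** Two bortezomib claims, two lenalidomide claims and one daratumumab claim satisfy every line of the penta-drug row. That is 1 + 1 + 1 = 3 agents, the same minimum as triple class. A rule requiring two different PIs, two different IMiDs and one CD38 antibody needs 2 + 2 + 1 = 5.

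**2. How the rules nest.** Take 0, 1 or 2 claims for each of the 3 PIs, 3 IMiDs and 2 CD38 antibodies. This gives 3^8 = 6,561 patterns.

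- Triple class: (27 − 1) × (27 − 1) × (9 − 1) = 26 × 26 × 8 = 5,408.
- Penta-drug as written (at least 2 claims per class means dropping the one empty pattern and the three single-claim patterns): 23 × 23 × 8 = 4,232.
- Agent-based (dropping the one empty pattern and the six one-agent patterns): 20 × 20 × 8 = 3,200.

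Every agent-based pattern meets the written rule, and every written-rule pattern is triple-class. There are no exceptions. The remaining 4,232 − 3,200 = 1,032 patterns meet the written rule without five-drug exposure. These count patterns, not patients. They settle the direction of error, not its size.

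**3. Size, under assumptions.** First, how close does the written rule come to triple class? Assume claims per exposed class follow a zero-truncated Poisson with parameter λ, independently for PIs and IMiDs. Then P(at least 2 | at least 1) = 1 − λe^(−λ) / (1 − e^(−λ)), and the share of triple-class patients who also meet the written rule is its square.

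| λ | One class | Both classes |
|---|---|---|
| 2 | 0.687 | 47% |
| 3 | 0.843 | 71% |
| 5 | 0.966 | 93% |
| 8 | 0.997 | 99.5% |

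Next, assume 90% of patients are triple-class exposed. Let q be the share of those with at least two claims in both classes, and s the share who truly had two PIs and two IMiDs. The overstatement is 0.90 × (q − s). The patient counts apply these shares to the 133 patients with an elranatamab claim reported in section 9.5. They are for scale only, because 133 is not the eligible cohort.

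| s | Agent-based, of 133 | Written rule, q = 0.92 | Written rule, q = 0.99 | Overstatement (points) |
|---|---|---|---|---|
| 0.30 | 36 | 110 | 119 | 55.8 to 62.1 |
| 0.50 | 60 | 110 | 119 | 37.8 to 44.1 |
| 0.70 | 84 | 110 | 119 | 19.8 to 26.1 |
| 0.90 | 108 | 110 | 119 | 1.8 to 8.1 |

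The ends of the range are 0.90 × (0.92 − 0.90) = 1.8 points and 0.90 × (0.99 − 0.30) = 62.1 points. With fewer claims per class the gap narrows: q = 0.71 and s = 0.30 give 0.90 × 0.41 = 36.9 points.

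**The case against.** The best defence is that the wording is ambiguous rather than wrong. The word distinct appears in the penta-drug row and not in the triple-class row, and any two claims are already distinct, so it may have been meant as claims for distinct drugs. The row's name, its 2 + 2 + 1 build and its pointer to the generic names support that intention. This stands as a guess at intent. It does not rescue the text, for three reasons.

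- The protocol uses claims elsewhere for billing records, for example when it counts pharmacy claims and index-drug claims in Table 3.
- Reading the phrase as distinct codes would not help. Annex 2 lists eight HCPCS codes and more than 30 NDCs for only three PIs.
- Section 9.8 says measures will be coded from the protocol's own algorithms and that the protocol will be followed strictly. A compliant programmer would count claims. A separate SAP could specify agents, but the protocol would still state a different rule.

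A second objection is that the row matters little. It does not enter eligibility, the Medicare-entitlement subgroups or any outcome, and prior PI, IMiD, antibody, CAR-T, BCMA-directed and transplant exposure are reported separately. This stands, and it limits the weight of the point.

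Stronger readings are tempting but not supported:

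- *The variable adds nothing to triple class.* The protocol gives no claims per patient. Under the model above, 47% of triple-class patients meet the written rule at λ = 2. Only 180 days of continuous enrolment before index are required, so some histories may be short.
- *The cohort will look more refractory.* The variable measures exposure. It says nothing about refractoriness.
- *Comparison with trial populations is distorted.* No such comparison is planned, and section 9.7 rules out formal comparisons between groups.

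**Conclusion.** The point holds as an error in a stated definition. As written, penta-drug exposure can be reached with three drugs, and the rule can only equal or exceed true five-drug exposure. That direction follows from the text alone and needs no assumption.

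The size cannot be determined from the protocol. The range of about 2 to 62 percentage points rests on three assumed quantities: 90% triple-class exposed, 92–99% of those with two or more claims in both classes, and 30–90% of them with two PIs and two IMiDs. No single value within it is better supported than another. Closeness to the triple-class percentage is plausible, because the look-back starts at MM diagnosis and the data reach back to 2016, but it remains an inference.

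The consequence is one descriptive Objective 1 percentage per cohort that may make patients look more heavily pre-treated than they were. No eligibility rule or outcome changes. It is worth correcting because the reported label would not match what was counted.

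**What to change.** In Table 2, redefine the row by agent: before index, claims for at least two different generic PIs (of bortezomib, carfilzomib and ixazomib), at least two different generic IMiDs (of lenalidomide, thalidomide and pomalidomide), and at least one claim for a CD38 antibody. State that agents are counted and that repeat claims for one agent count once. Map the PI and IMiD codes in Annex 2 to generic name so that the count can be programmed.

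The cost is one table row, a small mapping task (the codes are pooled by class at present) and a short code change. The percentage will be the same or lower. Version 2.0 already corrected a single mistyped daratumumab code, so a change of this scale has a precedent. By the milestone table, two interim analyses, the final analysis and the final report follow the date of version 2.0. If interim results produced before that date used the claim-based rule, a note should say that their percentage is not comparable with later ones.

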8. RESEARCH QUESTION AND OBJECTIVES

The overall aim of the study is to understand the real-world usage of elranatamab for the treatment of MM. To meet these objectives, the Clarify team will partner with Pfizer to create a curated dataset of Medicare FFS beneficiaries and their treatments to serve as the foundation upon which to examine descriptive data.

Specifically, the analysis will focus on the following primary research objectives:

Primary

- **Objective 1:** To describe the demographics, clinical history, and treatment history of patients treated with elranatamab
- Objective 2: To describe the administration and treatment management of elranatamab
 - Assess administration and management details (place of service, dosage, timing, frequency, supportive MM medication usage)
 - Evaluate dose, duration, and reasons for administration interruption or discontinuation, as available
- **Objective 3:** To describe all-cause and MM-related healthcare resource utilization (HCRU) and associated costs among patients treated with elranatamab

Exploratory

- Exploratory Objective 1: To describe the tolerability and real-world safety of elranatamab
- Exploratory Objective 2: To describe the overall effectiveness of elranatamab in terms of
- time to next treatment or death (TTNT/D) and overall survival (OS)
- Exploratory Objective 3: In a separate cohort, replicate all objectives for patients who initiated teclistamab

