9.2. Setting

This study will evaluate adult patients with RRMM who initiate elranatamab or teclistamab. Patients will enter (i.e., index) on the first observed elranatamab or teclistamab claim between August 14, 2023 and March 2025. Limited eligibility criteria will be applied.

Study Period: Start of data (Jan 1, 2016) to the most current, available data.

MM diagnosis window: Start of data (Jan 1, 2016) to index date

Index date: First elranatamab or teclistamab claim after initial MM diagnosis

Observability: At least 180 days of continuous closed-claims medical and pharmacy enrollment prior to index (inclusive) and 30 days after the index date

Baseline period for MM-related treatments and MM-related comorbidities: MM diagnosis to one day prior to index date

Charlson Comorbidity Index and baseline HCRU assessment window: 180 days prior to index date to index date

Follow-up: Index date until death, the earliest of end of study period, or end of continuous enrollment (unless otherwise noted). Alternative censoring criteria will be applied for certain outcomes (such as OS, TTD, and TTNT/D).

Figure 1 reflects the time periods of interest in the study cohort. The data end date in Figure 1 will be updated at the time of the second, third, and final analyses, estimating data through June, September, and December 2025, respectively. All other dates shown in the figure will remain the same for the subsequent analyses.

[figure not shown]

Figure 1. Study Schematic for Patients Receiving Elranatamab or Teclistamab

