2	Average time between elranatamab or teclistamab claims	Sum of the days between claims for the index drug (continuous) divided by the total number of administrations -1	Index date to the end of follow-up Step-Up Dosing Period

	1	T	T
			Maintenance Periods
2	Frequency of elranatamab or	Total number of inpatient, non-IP, and pharmacy claims of the index drug during the	Index date to the end of follow-up
	teclistamab claims	time period based on vial size (continuous)	Step-Up Dosing Period
			Maintenance Periods
2	Relative Administration Intensity (RAI)	The ratio of the actual administrations received divided by the expected number of administrations according to the US label	Index date to the end of follow-up
		(continuous)	Step-Up Dosing Period
			Maintenance Periods
2	Time to Discontinuation (TTD)	Time in months from first administration until last administration prior to treatment discontinuation (continuous). Treatment discontinuation is defined as an 8-week gap in elranatamab or teclistamab therapy, next treatment after index treatment (CAR-T, BsABs, bendamustine or belantamab), or death.	Index date to the end of follow-up
2	Reason for Discontinuation	Reason for treatment discontinuation used to estimate time to discontinuation, either an 8-week gap in elranatamab or teclistamab therapy, next treatment after index treatment (CAR-T, BsABs, bendamustine or belantamab), or death.	Index date to the end of follow-up
Health care	resource utilization an	d costs	
3	All-cause IP visits	Medical claim for IP (non-emergency department [ED]) visit (dichotomous)	Start of data to 1 day before index date, index date until last recorded dose, and time from discontinuation through time of censoring
		Number of IP (non-ED) visits (continuous)	
3	All-cause OP visits	Medical claim for non-IP/non-ED visit (dichotomous)	Start of data to 1 day before index date, index date until last recorded dose, and time from
		Number of non-IP/non-ED visits (continuous)	discontinuation through time of censoring

3	All-cause ED visits	Medical claim for ED visit (dichotomous) Number of ED visits (continuous)	Start of data to 1 day before index date, index date until last recorded dose, and time from discontinuation through time of censoring
3	All-cause pharmacy claims	Pharmacy claim (dichotomous) Number of pharmacy claims (continuous)	Start of data to 1 day before index date, index date until last recorded dose, and time from discontinuation through time of censoring

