3	Total duration of all-cause IP stays	The total time in days of IP stays among patients who have at least 1 IP stay (continuous).	Start of data to 1 day before index date, index date until last recorded dose, and time from discontinuation through time of censoring
3	Total all-cause HCRU	IP, OP, ED, or pharmacy claims (dichotomous) Number of IP, OP, ED, or pharmacy claims	Start of data to 1 day before index date, index date until last recorded dose, and time from discontinuation through
3	MM-related IP visits	(continuous) Medical claim for IP (non-ED) visit with an MM ICD-10 code or treatment for MM (dichotomous) Number of IP (non-ED) visits with an MM	Start of data to 1 day before index date, index date until last recorded dose, and time from discontinuation through time of censoring
3	MM-related OP visits	ICD-10 code or treatment for MM (continuous) Medical claim for non-IP/non-ED visit with an MM ICD-10 code or treatment for MM (dichotomous)	Start of data to 1 day before index date, index date until last recorded dose, and time from
		Non-IP/non-ED visits with an MM ICD-10 code or treatment for MM (continuous)	discontinuation through time of censoring

	1		
3	MM-related pharmacy claims	Pharmacy claim with a treatment for MM (dichotomous)	Start of data to 1 day before index date, index date until last recorded dose, and time from
		Number of pharmacy claims with a treatment for MM (continuous)	discontinuation through time of censoring
3	Total duration of MM-related IP stays	The total time in days of IP stays with an MM ICD-10 code or treatment for MM, among patients who have at least 1 IP stay (continuous)	Start of data to 1 day before index date, index date until last recorded dose, and time from discontinuation through time of censoring
3	Total MM-related HCRU	IP, OP, ED, or pharmacy claims with an MM ICD-10 code or treatment for MM (dichotomous)	Start of data to 1 day before index date, index date until last recorded dose, and time from discontinuation through
		IP, OP, ED, or pharmacy claims with an MM ICD-10 code or treatment for MM (continuous)	time of censoring
3	Cost of all-cause IP visits	Cost of IP (non-ED) visits (continuous)	Start of data to 1 day before index date, index date until last recorded dose, and time from discontinuation through time of censoring

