9.7.3. Healthcare Resource Utilization and Cost

All-cause HCRU and MM-related HCRU (i.e., HCRU with a diagnosis code or treatment for MM) will be measured as the total number of per-patient-per-month (PPPM) IP, OP, ED, and pharmacy claims that occurred over the follow-up period. Medical claims will only be counted once per day to estimate visits. Additionally, the total length of IP stays will be reported among patients with at least one IP visit. Given the recency of the study period, costs will not be adjusted for inflation.

HCRU and costs will be measured across three different time periods: from the start of data to a day before the index date, from the index date until last recorded dose, and the time from discontinuation through the time of censoring. Patients will be censored at the earliest of death, next treatment (CART, BsABs, bendamustine or belantamab), the end of part A or B continuous closed-claim coverage, or the end of data.

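### For PIs, IMiDs, mAbs, non-bendamustine chemotherapies, venetoclax and selinexor, a single post-index yes/no window merges use alongside the index drug with use after it

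*Protocol*

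**What the plan says.** Table 2 in section 9.3 gives each myeloma drug class two assessment periods: one before index, and one after it, "Index date to the end of follow-up". The variable is a patient-level flag. The IMiD row, for example, asks for a claim "in the non-IP or pharmacy setting for lenalidomide, thalidomide, or pomalidomide (dichotomous").

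Section 9.2 defines follow-up as "Index date until death, the earliest of end of study period, or end of continuous enrollment (unless otherwise noted"). Stopping the index drug does not end it.

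Other parts of the Protocol do mark the end of index treatment:

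- Table 3, time to discontinuation (TTD): "Treatment discontinuation is defined as an 8-week gap in elranatamab or teclistamab therapy", or "next treatment after index treatment (CAR-T, BsABs, bendamustine or belantamab), or death".
- Section 9.7.3, resource use and costs: after the pre-index period, time is divided into two, "from the index date until last recorded dose, and the time from discontinuation through the time of censoring".

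**The concern.** Section 8 states the purpose: "The overall aim of the study is to understand the real-world usage of elranatamab for the treatment of MM". Section 7 describes the pivotal elranatamab trial as a test of monotherapy. Two natural questions for a usage study are whether patients receive the drug alone or with another anti-myeloma class, and which classes they receive once it stops.

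Under the Table 2 definition, a pomalidomide claim in the third week of elranatamab and a pomalidomide claim a year after the last dose produce the same yes. A reader of the results table could take the percentage as combination use, as later therapy, or as any mixture of the two. The longer the follow-up, the more later therapy is added to the same cell.

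**Working it through.** The Protocol gives no figure to reproduce here, so the check is mainly a comparison of passages.

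**1. Does the window cover both phases?** Inputs: index from 14 August 2023 to March 2025 (section 9.2; 31 March assumed), data to December 2025 (section 9.1; 31 December assumed), and 30.4375 days per month (section 9.7.5).

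- Earliest index: 14 August 2023 to 31 December 2025 = 870 days; 870 / 30.4375 = 28.6 months.
- Latest index: 31 March 2025 to 31 December 2025 = 275 days; 275 / 30.4375 = 9.0 months.
- Discontinuation gap: 8 × 7 = 56 days.

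These are maxima before death or disenrolment. With an index date by March 2025, every patient has potential follow-up well beyond one 56-day gap. Inclusion criterion 1 in section 9.2.1 instead lets index run to the latest available data; patients indexed that late would have much less.

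**2. Does another variable recover the split by class?**

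| Variable | Cut at end of index treatment? | Identifies PIs, IMiDs, mAbs, other chemotherapies, venetoclax, selinexor? |
|---|---|---|
| Table 2 class rows | No | Yes |
| TTD and reason for discontinuation (Table 3, 9.7.5) | Yes | No; only CAR-T, BsAbs, bendamustine and belantamab are named |
| TTNT/D (Table 3, 9.7.7) | Event is the next treatment | No; same four |
| MM-related resource use (Table 3, 9.7.3) | Yes | No; all myeloma treatments are pooled, e.g. "Pharmacy claim with a treatment for MM (dichotomous") |

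No row has both properties for these classes.

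**3. How wide is the ambiguity?** Let x be the patients flagged for a class, a those with a claim during index treatment, b those with a claim after it, and c those with both. Then x = a + b − c. Only x is reported, so a can be anything from 0 to x. The lower end requires that every flagged patient has follow-up after the last dose.

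Illustration with N = 133, the number of patients with an elranatamab claim in August 2024 (section 9.5), and assumed usage rates:

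| Assumed rate | x | Possible a |
|---|---|---|
| 10% | 13 | 0 to 13 |
| 20% | 27 | 0 to 27 |
| 30% | 40 | 0 to 40 |
| 40% | 53 | 0 to 53 |

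For x = 40, the Wilson interval is [p + z²/2n ± z√(p(1−p)/n + z²/4n²)] / (1 + z²/n), with p = 40/133 = 0.301, z = 1.96 and n = 133. This gives 22.9% to 38.3%. It expresses sampling error in the pooled flag and says nothing about how the 40 divide.

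**The case against.** The Table 2 rows are clear and contradict nothing. No objective promises a monotherapy share or a class-level sequence. Section 9.7 allows further segmentations and leaves detailed methods to an SAP that is not at hand. This stands in part: the point is an improvement, not an error. But the Protocol itself fixes the assessment period for each row, and section 9.8 commits to following the Protocol strictly. The latitude in section 9.7 distinguishes pre-index from post-index time and mentions no division within the latter.

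Three stronger readings are tempting, and the document does not support them.

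- **That every post-index drug row is affected.** CAR-T, BsAbs (hence talquetamab), belantamab and bendamustine are next treatment by rule, and starting one ends index treatment. Those rows need no split. Steroids are a separate case: Annex 2 lists dexamethasone as premedication, and the supportive-medication row in Table 3 has its own dosing periods. The drug list of that row is missing from the text at hand, so nothing firm can be said about steroids.
- **That the information is lost.** Claims are dated. The limit lies in the variable as defined, not in the data.
- **That effectiveness, safety and cost results become unreadable.** Those analyses are unadjusted descriptions with no formal comparison between groups. Splitting the Table 2 rows would alter none of them; it would only add a description of co-treatment beside them.

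**Conclusion.** The point holds for PIs, IMiDs, mAbs, chemotherapies other than bendamustine, venetoclax and selinexor. As planned, the study can report how many patients had each class at some time after index, but not how many had it with the index drug and how many after it.

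The ambiguity can be as wide as the reported percentage itself. That follows from using a pooled flag and holds at any usage rate; the 30% of 133 example is illustrative only, since the Protocol gives no usage rate and 133 predates both eligibility screening and the data extension. The effect is confined to the description of real-world use. This is a worthwhile, inexpensive refinement rather than a flaw that invalidates a planned result.

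**What to change.** For the listed classes, replace or supplement the post-index window in Table 2 with two:

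- **(a) During index treatment:** index date to last recorded dose, the cut already used in section 9.7.3. For patients still on treatment, end the window at their censoring date.
- **(b) After index treatment:** the day after the last recorded dose to end of follow-up, with patients who discontinued alive as the denominator. Discontinuation includes death, so using all who discontinued would bring in patients with no later period.

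Report the share of patients with none of these non-steroid classes in (a) as use without another anti-myeloma class. Tabulate steroids separately, because a premedication claim for dexamethasone would otherwise make a patient look like a combination user.

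Cite last recorded dose as the cut rather than section 9.7.5, which measures to the date of discontinuation and is conditional on follow-up being judged adequate. State which dose counts when a patient restarts after an 8-week gap.

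The cost is a change to the Table 2 wording and a date filter on a date that section 9.7.3 already needs. Smaller cells may fall more often under the CMS rule in section 9.4 against reporting counts of 1 to 10; keeping the pooled row alongside limits that loss.
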